13. STATISTICAL CONSIDERATIONS

Age-corrected 100M will be considered as the primary outcome, and will be evaluated using a two-one-sided t-test to test equivalency between treatment arms in the change from baseline to 6 months. In addition, repeated measures ANOVA will be used to determine whether the trajectory across all three time points (baseline, 3mo, 6mo) differs by treatment group. Strength testing/dynamometry, NSAA, 4-stair climb, and time to arise from floor scores will be secondary outcomes, and will also be compared by treatment group using repeated measures ANOVA. Biomarkers studies will be considered exploratory outcomes.

Power: Prior studies evaluating the 100m walk test among patients with DMD have shown an average change over 6 months of -2.9 ± 7.8 . An effective sample size of 10 patients per group will provide 80% power to declare equivalency with an equivalence margin of $\pm 10.6^{21}$.

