7.2 Study Population

DMD patients (n =24) will be enrolled in a randomized open label controlled trial of prednisolone (n= 10) versus spironolactone (n = 10) based on inclusion criteria as defined below. Four to seven collaborating centers will participate. Up to 24 subjects (~ 3 at each site) can be enrolled to include a 10% drop-out rate.

Power: Prior studies evaluating the 100m walk test among patients with DMD have shown an average change over 6 months of -2.9 ± 7.8 . An effective sample size of 10 patients per group will provide 80% power to declare equivalency with an equivalence margin of $\pm 10.6^{21}$.

Siblings will be permitted to participate. When sibling participation arises, the randomization will proceed as if they were unrelated.

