8.4 Baseline Assessment of Endpoints

After obtaining informed consent and completing the registration procedures, baseline subject history data will be collected, including records of all medications and supplements that the subject is taking. The following assessments will be performed to confirm subject eligibility for this trial. Screening tests must be completed prior to treatment administration as described in the study timeline. Screening testing includes the following, which are discussed in detail below:

- 100 meter timed test (100M)
- Strength testing and dynamometry
- North Star Ambulatory Assessment (NSAA)
- 4-stair climb
- Time to arise from floor
- Echocardiogram
- Baseline laboratory testing

The subject and his parents will be aware that his participation may be terminated after any of these screening procedures.

There is no central laboratory for this trial. Site-specific normal lab ranges will be documented in respective sites' regulatory binders. Lab ranges will be provided by each site's laboratory. Laboratory tests with values within the clinically significant range will be repeated during the same visit whenever possible. If the test result returns after the subject leaves the clinic, they will be immediately contacted. Subjects will be asked to return to the outpatient clinic for a repeat test. For non-local subjects, arrangements can be made to have the blood test redrawn in a laboratory close to home or by their primary care physician. If still out of the range and clinically significant, the subject may be terminated from the study following discussion with the Clinical Safety Monitor.

To avoid any confusion for the primary care physician, he or she will be informed (with permission from the subject) of their participation in the trial at the time of enrollment.

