10.2 Study Visits

10.2.1 Timeline

Table 3 Schedule of Assessments

Assessment	Visit 1	Study Drug Start ¹	Visit 2	Visit 3	Visit 4	Visit 5	Visit 6	Visit 7	Visit 8
	Screening		Week 1	Month 1	Month 2	Month 3	Month 4	Month 5	Month 6
	Day -14 to 0		Day 0	Day 7	Day 30	Day 60	Day 90	Day 120	Day 180
Research Purposes Only									
Echocardiogram (Echo) ²	X								X
Biomarkers Blood Draw (plasma and white blood cells)	X								X
Strength Testing/Dynamometry	X					X			X
Standard of Care									
Informed Consent	X								
AE Assessment		X	X	X	X	X	X	X	X
Concomitant Medications	X	X	X	X	X	X	X	X	X
Physical Exam	X					X			X
Skin Exam	X					X			X
Cushingoid Exam	X					X			X
Medical History Review	X					X			X
100 Meter Timed Test	X					X			X
Parent Survey			X	X	X		X	X	
4-Stair Climb	X					X			X
North Star Ambulatory Assessment (NSAA)	X					X			X
Time to Arise from Floor	X					X			X
Creatine Kinase	X								X
Gamma Glutamyl Transferase (GGT)	X					X			X
Creatinine	X					X			X
Blood Urea Nitrogen (BUN)	X					X			X
Glucose	X					X			X
Cystatin C	X					X			X
Electrolytes ³	X		X	X	X	X	X	X	X
Medication Dispensing ⁴		X ¹				X			
Vitals	X					X			X

1. Study drug will be dispensed and treatment initiated once eligibility is confirmed following receipt and review of results from screening visit procedures. The day study drug is started is considered Day 0.

2. A clinical echocardiogram within the previous 30 days prior to screening is acceptable for screening purposes.
3. Includes: Sodium, Potassium, Chloride, CO₂
4. Medication dispensing will occur every 90 days, beginning at the time of randomization.

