10.3 Day -14 to Day 0 (Screening Evaluations and First Dose)

Informed consent will be obtained prior to the collection of any data and any study-related procedures. Screening evaluations will be obtained. Subjects will undergo a physical, skin, and cushingoid examination, vitals and a review of medical and concomitant medication histories. Echocardiogram, strength testing/dynamometry, and functional testing (100 meter timed test [100M], North Star Ambulatory Assessment [NSAA], 4-stair climb, and time to arise from floor test) will be conducted.

Lab work will include the following:

- Creatine Kinase
- Gamma-glutamyl transferase (GGT)
- Creatinine
- Blood Urea Nitrogen (BUN)
- Glucose
- Serum Cystatin C
- Electrolytes
- Biomarkers blood draw (for plasma and white blood cells)

Once eligibility has been confirmed (including lab results and echocardiogram review), the pharmacy will dispense a 90-day supply of study medication to the research team who will then provide the study medication to the subject's parent/guardian. If eligibility cannot be confirmed on the same day of screening, the study drug may be shipped to the subject and a pharmacist will counsel the parent or guardian via phone. The day study drug treatment is initiated is considered Day 0.

10.4 Week 1 and Month 1 and 2

Subjects will be contacted by research staff via a REDCap survey to review concomitant medications and assess adverse events.

Lab work will include the following:

- Electrolytes

10.5 Month 3

Subjects will return on Month 3 and undergo a physical, skin, and cushingoid examination, vitals. Strength testing/dynamometry, and functional testing (to include 100 meter timed test, North Star Ambulatory Assessment [NSAA], 4-stair climb, and time to arise from floor test) will

be conducted. Research staff will also review concomitant medications, updates to the medical history, and assess adverse events.

Lab work will include the following:

- Gamma-glutamyl transferase (GGT)
- Creatinine
- Blood Urea Nitrogen (BUN)
- Glucose
- Cystatin C
- Electrolytes

The pharmacy will dispense the supply of study medication to the research team who will then provide the study medication to the subject's parent/guardian. If lab results return after the subject leaves the clinic and the Study Doctor wants additional tests, they will be immediately contacted.

10.6 Month 4 and 5

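### Optional improvement, not an error: the primary equivalence test on change in 100M uses no baseline covariate, although every boy has a baseline 100M; adjustment handles chance imbalance, but a power gain cannot be promised from the documents

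*Combined protocol and SAP*

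**What the plan says.** The synopsis and Section 13 describe the deciding analysis in the same words: age-corrected 100M "will be evaluated using a two-one-sided t-test to test equivalency between treatment arms in the change from baseline to 6 months". Neither place names a covariate, and no other section adds one.

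A second 100M analysis is planned: "repeated measures ANOVA will be used to determine whether the trajectory across all three time points (baseline, 3mo, 6mo) differs by treatment group". It treats baseline as one of three outcome time points and is not the equivalence test.

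The baseline value exists for every boy. Sections 8.4 and 10.3 list 100M among the screening tests done before treatment. The row "100 Meter Timed Test" in Table 3 (Section 10.2.1) is marked at screening, Month 3 and Month 6.

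The power statement appears in the synopsis, Section 7.2 and Section 13. "Prior studies evaluating the 100m walk test among patients with DMD have shown an average change over 6 months of" −2.9 ± 7.8, and "An effective sample size of 10 patients per group will provide 80% power to declare equivalency with an equivalence margin of" ±10.6. Section 7.2 adds that up to 24 boys "can be enrolled to include a 10% drop-out rate".

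**The concern.** A change-score comparison subtracts the whole baseline value, so it fixes the slope of Month 6 on baseline at 1. ANCOVA estimates that slope. If the true slope differs from 1, baseline still predicts change, and the planned test leaves that variation in its error term.

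Two things follow in a trial of 10 to 12 boys per arm. First, the width of the 90% CI largely decides whether equivalence is declared, so any recoverable precision counts. Second, Section 8.3 describes 1:1 randomization at each site and no stratification by baseline function, so chance imbalance is likely. Under simple randomization (an approximation) at 10 per arm, the difference in baseline means has standard error √(2/10) = 0.447 baseline SD. A difference of half an SD or more then occurs in about 26% of trials. If baseline correlates with change by ρ, such an imbalance shifts the change-score difference by ρ × 7.8 × imbalance in SDs. At ρ = 0.4 and an imbalance of 0.8 SD that is 0.4 × 7.8 × 0.8 ≈ 2.5, against a margin of 10.6.

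The age correction does not deal with this, because it adjusts for age and not for the boy's own starting time.

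**Working it through.** **Inputs from the documents.** Change SD 7.8 (the figure after ± read as an SD), margin ±10.6, 10 evaluable per arm, 1:1 allocation, 24 enrolled with 10% drop-out.

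**Assumptions not in the documents.** Alpha 0.05 per side, true difference 0, equal slopes in the two arms, 7.8 and ±10.6 applicable to the analysed scale, and the ranges below for the baseline-to-Month 6 correlation r and for k = Month 6 SD ÷ baseline SD.

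**Step 1: reproduce the planned power.** SE = 7.8 × √(2/10) = 3.49, with 18 df and critical t = 1.734. Integrating the two one-sided tests over the distribution of the variance estimate gives 79.8%, against 80% stated. Alpha 0.025 gives 63.9%, and a true difference of 2.9 gives 66.5%. The stated figure therefore fits alpha 0.05 per side, no true difference and no covariate.

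**Step 2: ANCOVA power by baseline-to-change correlation ρ.** Residual SD = 7.8 × √(1 − ρ²). The SE is inflated by √(1 + 1/(N − 4)), which is √(1 + 1/16) = 1.031 at N = 20. There are N − 3 = 17 df, with critical t = 1.740. At 10 per arm:

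| \|ρ\| | 0 | 0.2 | 0.25 | 0.3 | 0.4 | 0.5 |
|---|---|---|---|---|---|---|
| ANCOVA power | 76.3% | 78.5% | 79.8% | 81.3% | 85.0% | 89.5% |

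The break-even is |ρ| = 0.252, where baseline explains about 6% of the variance of change (0.252² = 0.064).

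**Step 3: largest possible loss (ρ = 0).**

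| Per arm | Change score | ANCOVA | Loss | Break-even \|ρ\| |
|---|---|---|---|---|
| 10 | 79.8% | 76.3% | 3.5 points | 0.252 |
| 11 | 84.8% | 82.1% | 2.7 points | 0.237 |
| 12 | 88.6% | 86.5% | 2.0 points | 0.225 |

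Twenty-four boys with 10% drop-out leave 24 × 0.9 = 21.6, or about 11 per arm.

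**Step 4: what ρ means in terms of r and k.** ρ = (rk − 1)/√(1 + k² − 2rk). With the change SD fixed at 7.8, each pair also implies a baseline SD of 7.8/√(1 + k² − 2rk). At 10 per arm, each cell gives ANCOVA power, with the implied baseline SD in brackets:

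| k | r = 0.3 | r = 0.5 | r = 0.7 | r = 0.9 |
|---|---|---|---|---|
| 0.9 | 96.1% (6.9) | 93.0% (8.2) | 89.4% (10.5) | 86.5% (17.9) |
| 1.0 | 93.7% (6.6) | 89.5% (7.8) | 84.5% (10.1) | 79.1% (17.4) |
| 1.1 | 91.3% (6.3) | 86.2% (7.4) | 80.7% (9.5) | 76.3% (16.3) |
| 1.2 | 88.9% (5.9) | 83.4% (7.0) | 78.2% (8.9) | 77.6% (14.7) |

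With equal SDs, |ρ| = √((1 − r)/2). The break-even is therefore r = 1 − 2 × 0.252² = 0.873, an implied baseline SD of 7.8/(2 × 0.252) ≈ 15.5. ANCOVA loses for r above 0.87 at k = 1.0, for r from 0.73 to 0.97 at k = 1.1, and for r from 0.63 to 0.93 at k = 1.2. If k is below √(1 − 0.252²) = 0.968, no r gives a loss.

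**Step 5: simulation check.** Forty thousand simulated trials per setting at 10 per arm agreed. For example, at k = 1.0 and r = 0.5 the change score had 80.2% and ANCOVA 89.4%; at k = 1.1 and r = 0.9, 79.8% and 76.1%. With right-skewed data the direction was the same at k = 1.0, r = 0.5 (78.9% and 86.2%). At a true difference of 10.6, the ANCOVA type I error was 0.048 to 0.053 with normal data and 0.045 to 0.049 with skewed data. Unequal slopes between arms were not simulated.

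**The case against.** The strongest case on the other side is that this is a preference. Under randomization the change-score difference is unbiased for the same treatment effect, and Section 13 sizes the trial for exactly the test it names. For a pilot that is a coherent choice. This stands. A reader might infer that the planned test is wrong or underpowered, and the documents do not support that.

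The second objection is that the sign of the power effect is unknown. This also stands. A reader might infer that ANCOVA will gain power except in a corner case. The loss region, however, is where Month 6 time tracks baseline time closely, which is plausible for a repeatable timed test. At r = 0.7 the effect is +4.7 points with equal SDs, +0.9 at k = 1.1 and −1.6 at k = 1.2. The gain of 9.7 points at r = 0.5 with equal SDs needs boys to vary at baseline no more than their changes vary (both SDs 7.8).

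Third, a reader might take comfort that the worst case stays above 80%. That holds at 11 per arm (82.1%) but not at the 10 per arm of the power statement (76.3%). It also assumes no true difference: at a true difference of 2.9 and 10 per arm, the figures are 66.5% for the change score and 63.4% for ANCOVA with an uninformative baseline.

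Fourth, the age correction may already remove part of what baseline would explain. Its method is not defined, so the remaining correlation is unknown. This is one more reason not to promise a gain.

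What the objections do not remove is that the loss is small and capped, the covariate is already collected, and adjustment removes the linear effect of chance imbalance.

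**Conclusion.** The plan contains no error here. The primary test is valid and its power reproduces at 79.8%. Baseline adjustment is a reasonable, inexpensive improvement whose power effect cannot be sized from the documents. At 10 per arm it gains when baseline and change correlate by more than about 0.25 in either direction, and otherwise costs at most 3.5 points. At 11 and 12 per arm the maximum cost is 2.7 and 2.0 points.

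These figures rest on alpha 0.05 per side, no true difference, a change SD of 7.8 and equal slopes. The first two are inferred from reproducing the stated power. Whether 7.8 and ±10.6 are on the age-corrected scale is not stated, but that is a separate documentation question; it affects both tests alike and adds no weight to this point.

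Severity: optional, low-cost recommendation.

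**What to change.** Before adopting the change, check r and the baseline and Month 6 SDs in the prior 100M data behind the power statement, if the sponsor has access to them. If baseline and change correlate by less than about 0.25, keeping the planned test is defensible.

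If adopted, pre-specify in Section 13 and the synopsis:

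- The primary analysis is an ANCOVA of Month 6 age-corrected 100M on arm and baseline age-corrected 100M.
- Equivalence is declared if the 90% CI of the adjusted arm difference lies within ±10.6. The 90% level matches alpha 0.05 per side.
- The change-score two one-sided t-test is a sensitivity analysis, and the ANCOVA decides.

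Add a note at each power statement (synopsis, Section 7.2, Section 13) that the 80% was computed for the unadjusted change-score test. The choice should be fixed before outcome data are seen, because the trial is open label.

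The cost is a short edit in two places, a note in three, and no new data. The analysis spends one degree of freedom. If baseline barely predicts change, it gives up the small amount of power stated above, which at 10 per arm would leave it below the planned 80%.

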The pilot trial we propose will directly answer the question of whether spironolactone is as efficacious as prednisolone over 6 months of treatment in young patients (age ≥ 4 to ≤ 7 years) with DMD, as judged by the age-corrected 100 meter timed test and by dynamometry scores derived maximum voluntary isometric contraction testing of selected muscles and the time to climb 4 stairs. For steroid-naïve patients, this could delay institution of prednisolone therapy – considered the standard of care – for up to 6 months. However, it is important to recognize that not all DMD parents choose for their boys to go on steroids during this age window, and that there is no clear evidence based consensus of when treatment must be initiated. Finally, we note that published data from [name] lab and others demonstrates that prednisolone results in increased cardiac deterioration in the mdx mice, suggesting cardio-toxic effects on dystrophic heart^{11, 17}. Therefore, we feel that delaying onset of steroid therapy is justified for this pilot trial in order to gain meaningful pilot data regarding spironolactone in DMD patients, and note that all subjects will be offered open label prednisolone therapy as a standard of care after completion of the trial. If there is equal or greater efficacy with spironolactone, they may choose to continue on spironolactone.

In this pilot trial we will use prednisolone since it is delivered as an oral suspension. Since the standard of care regimen (daily versus weekend dosing of prednisolone) differs from site to site, each PI will have the discretion to assign subjects to their preferred regimen. Equal efficacy has been shown between daily and weekend dosing regimens¹⁸.

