8.1 Subject Inclusion Criteria

Subjects must meet all of the following Inclusion Criteria:

1. Duchenne muscular dystrophy (DMD) patients ≥ 4 to ≤ 7 years of age
2. Clinical features of DMD that include proximal predominant weakness and/or gait disturbance

3. Presence of a truncating mutation of the *DMD* gene in the patient or an affected male relative OR a muscle biopsy that demonstrates <5% dystrophin in the patient or an affected male relative
4. Normal left ventricular ejection fraction by screening echocardiogram
5. Ability to cooperate for testing
6. No prior treatment with glucocorticoids or vamorolone
7. No concomitant experimental therapies

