11.4 Study Discontinuation Rules

An independent Clinical Safety Monitor will monitor safety data on a continual basis throughout the trial. The Clinical Safety Monitor can recommend early termination of the trial for reasons of safety. Study enrollment will be halted by the Principal Investigators when any subject experiences a Grade 3 or higher adverse event toxicity that is unanticipated and possibly, probably, or definitely related to the study drug that presents with clinical symptoms and requires medical treatment. This will include any subject death, hospitalization, or important clinical laboratory finding. If after review by the Clinical Safety Monitor and the Reviewing IRB, the decision is made to continue, the trial will proceed according to Section 10 of this protocol.

Anticipated adverse events related to progression of Duchenne muscular dystrophy may include muscle weakness, elevated creatine kinase levels, loss of ambulation, scoliosis, short stature, and intellectual disability.

Anticipated adverse events related to prednisolone treatment, which is the standard of care, may include weight gain, cushingoid features, long bone fractures, acne, behavioral disturbance, and short stature (see section 9.3.2 for additional potential side effects).

Anticipated adverse events related to spironolactone treatment may include increased potassium levels, increased breast tissue mass, diarrhea, cramping, nausea, vomiting, headache, sleepiness, unsteadiness, and urticaria (see section 9.3.1 for additional potential side effects).

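### Section 13 gives no value to a boy who attempts the stair climb or the rise from floor and cannot do it, so under a plain analysis of times his loss of function may not count against his arm

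*Combined protocol and SAP*

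**What the plan says.** Section 13 (and the synopsis) lists the secondary outcomes: "Strength testing/dynamometry, NSAA, 4-stair climb, and time to arise from floor scores will be secondary outcomes". These "will also be compared by treatment group using repeated measures ANOVA", with visits at baseline, 3 and 6 months. Section 5.1 describes the stair test as "the time to climb 4 stairs" and names it, with the 100M and dynamometry, among the measures by which equal efficacy is to be judged. The rise test is a time by name.

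No section gives a cap, worst value, rank, speed conversion or separate category for a boy who attempts a timed test and cannot complete it. There is also no missing-data method and no analysis set.

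The only functional entry requirement in Section 8.1, beyond the clinical features of the disease, is "Ability to cooperate for testing". Section 11.4 says that anticipated events from disease progression "may include muscle weakness, elevated creatine kinase levels, loss of ambulation, scoliosis, short stature, and intellectual disability". Section 18.1 mentions a Manual of Operating Procedures, which is not among the documents.

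**The concern.** A failed attempt has no time. Classical repeated measures ANOVA needs a value at every visit, so one blank would remove the boy from all three. Software that keeps his other visits would still give the failure itself no weight. Either way the poorest result on the scale becomes a blank, and the reason for the blank is the outcome being studied.

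The trial aims to show that two treatments are similar, and Section 5.1 accepts that prednisolone may be delayed by up to 6 months in one arm. An analysis that can overlook loss of function is therefore weak where a reader most needs it. The trial is also open label, so a rule chosen after the data are seen could be chosen knowing the arm.

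**Working it through.** **The plan's own figure.** The plan gives no figure for the timed secondary tests. Its one power statement, for the 100M, reproduces. With SD 7.8 and 10 per group, the standard error is 7.8 × √(2/10) = 3.49. With margin ±10.6, true difference 0, 18 degrees of freedom and one-sided alpha 0.05 (assumed, since none is stated), exact power of the two one-sided tests is 79.8% against the stated 80%. This does not bear on the present point.

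**Inputs for the illustration.** Twelve per arm is from Section 7.1. The rest is assumed, because the documents give no distribution for these tests and no rate of loss:
- median rise time 6 s;
- log-scale SD 0.4 between boys and 0.2 for the 6-month change;
- arms otherwise identical, but two boys in one arm lose the task by Month 6 and none in the other;
- a common log-scale improvement *d* of 0, 0.1 or 0.2 in both arms.

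Mean baseline speed is (1/6) × exp(0.4²/2) = 0.18 per second.

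**Two analyses of the same data** (20,000 simulated trials per row; baseline to Month 6 only, as a simplification of the three-visit model):
- Time: mean of (Month 6 − baseline) among boys with a value, losing arm minus other arm. Negative means the losing arm looks better.
- Speed: mean of (1/time at Month 6, or 0 if unable, − 1/time at baseline), losing arm minus other arm, as a percentage of mean baseline speed. Negative means the losing arm looks worse.

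| Boys who lose the task | *d* | Time (s) | Speed (%) |
|---|---|---|---|
| Slowest at Month 6 | 0 | −0.23 | −8.5 |
| | 0.1 | −0.14 | −9.5 |
| | 0.2 | −0.05 | −10.6 |
| Slowest at baseline | 0 | −0.01 | −9.4 |
| | 0.1 | +0.06 | −10.2 |
| | 0.2 | +0.14 | −11.5 |
| Largest worsening | 0 | −0.42 | −11.0 |
| | 0.1 | −0.37 | −13.1 |
| | 0.2 | −0.33 | −16.4 |

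**Why the sign can turn.** For a boy with baseline time *b*, the expected change is *b* × (exp(−*d* + 0.2²/2) − 1). With *d* = 0.1 the factor is exp(−0.08) − 1 = −0.077, so slow boys improve by more seconds than fast ones. Removing those slowest at baseline then takes away the largest expected improvements, and the arm looks worse on time.

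**Scale.** The model is multiplicative. The percentages therefore do not depend on the assumed 6 s, and the differences in seconds scale with it. The same percentages would hold for the stair climb if its log-scale SDs were the same.

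**Noise.** The trial-to-trial SD of the time difference is about 0.5 to 0.6 s. In the first row about 65% of simulated trials favoured the losing arm.

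**Chance that the gap matters.** The probability of at least one inability among 24 boys is 1 − (1 − *p*)^24. For an assumed per-boy risk *p* of 1%, 2%, 5% or 10% it is 21%, 38%, 71% or 92%.

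**The case against.** A reader might infer that the plan drops the worst results and that this always favours the arm that lost function. The documents support neither statement.

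- **Removal is inferred from silence.** Section 13 names a method, not its handling of blanks, and speaks of scores. A cap or an inability code could sit in the operating manual or on the eCRF, whose fields are not shown. This stands, and the point has to be conditional. A test manual would not by itself settle the analysis, however, and Section 13 does not refer to one.
- **The direction is not fixed.** The table shows almost no bias when the boys lost were slowest at baseline, and bias against their arm when both arms also improve. Improvement is what the synopsis objective anticipates. This stands in full.
- **The trigger is assumed.** Two of 12 in one arm and none in the other, within 6 months at ages 4 to 7, is a chosen scenario. Section 11.4 lists what may occur and does not predict loss of ambulation during follow-up. Section 5.2 places that loss by age 12. This stands.
- **Speed with 0 is one choice among several.** A worst-rank analysis would also close the gap, and part of the 8% to 16% deficit comes directly from assigning 0. That is true, but 0 is the natural limit of speed as time grows. Unlike the analysis of times, speed with 0 showed the deficit in every scenario.
- **These are secondary outcomes in a 24-boy pilot.** Power to detect effects of this size is low, about 6%. The argument is about freedom from bias, not about significance.

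**Conclusion.** The concern holds in conditional form. The plan assigns no value to a boy who attempts the stair climb or the rise and cannot do it. If he is treated as missing, his loss of function does not count against his arm.

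Under the assumed inputs, with two of 12 boys lost in one arm, the time analysis is off by anything from about 0.4 s in favour of that arm to 0.14 s against it. Speed with 0 for unable shows that arm worse by about 8% to 16% of baseline speed in every row. The size in this trial cannot be derived from the documents, and if no boy loses a task the point has no consequence.

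The same silence applies to the primary 100M time, which is to be "evaluated using a two-one-sided t-test to test equivalency between treatment arms in the change from baseline to 6 months". A change at Section 13 is worthwhile because it is cheap and best made before data are seen. It is not a reason to question the primary design.

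**What to change.** In Section 13, state that 4-stair climb and time to arise from floor are analysed as speed (4 stairs/time; 1/time), with 0 when the boy attempts the task and cannot complete it. On the eCRF, distinguish 'unable' from 'refused or not done', if it does not already do so. Only 'unable' scores 0. Report the number unable per arm and visit. If the operating manual already holds a scoring rule, cite it and make the two agree.

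Add the same speed-based sensitivity analysis for the 100M (100 m/time, 0 if unable), and leave the primary equivalence test on its stated scale. The ±10.6 margin does not carry over to speed, so this analysis should give an estimate and interval, not an equivalence claim.

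The cost is a short addition to Section 13 and at most one eCRF code. Results per second are less familiar, so times should still be tabulated for boys who complete the task.
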